#### **4.2. Assessment for Decision-Making Capacity**

The independent psychiatrist or neurologist will meet with the potential subject prior to any study-related activities and review elements of the study with the patient discussing the potential benefits and risks. The independent psychiatrist or neurologist will conduct a thorough assessment of the decision-making capacity of the subject to determine if the subject understands and are able to appropriately judge the potential risks of the study and is able to provide informed consent. The subject will be interviewed to determine if he/she understands the research project and procedures, appreciates the effects of research participation on his/her own situation, is able to reason about participation and is able to communicate a choice about participating in this study. If the potential subject shows mild deficits in any one of these areas (understanding, appreciation, reasoning and choice), the independent psychiatrist or neurologist may provide feedback with multiple learning trials, since previous studies have demonstrated that such interventions can improve subjects' decision-making (33).

#### **4.3. Visit 1 – Baseline Visit #1**

After the subject has been determined to have decision-making capacity to provide informed consent, the following assessments must be conducted at Visit 1:

- Written informed consent
- Review inclusion and exclusion criteria
- Detailed medical history including review of medical records, current medications and duration of prior TS medication trials
- DSM-IV SCID to determine subject has diagnosis of TS by one study psychiatrist or neurologist (first evaluator), for ages 15-17 this will be the K-SADS assessment.
- Complete physical examination including height, weight and vital signs

Date: 2/24/2021

Principal Investigator: [name], PhD

Application Number: NA\_00073086

- EKG, blood samples (CBC, and complete metabolic panel) for clinical laboratory tests
- Urine sample for urine toxicology screen and urine pregnancy test (for females)
- TS symptom scales, including the Yale Global Tic Severity Scale (YGTSS), the Yale-Brown Obsessive Compulsive Scale (YBOCS) for OCD symptoms, and the WHO Adult ADHD Self-Report Scale (ASRS) for ADHD symptoms.
- Assessment of depression, anxiety, or symptoms of mania using the Hamilton Depression Rating Scale (Ham-D), the Beck self-reporting Anxiety Inventory (BAI), and the Young Mania Rating Scale (YMRS). For ages 15-17, the Ham-D and BAI scales will be replaced with the Beck Youth Inventory.
- Columbia Suicide Severity Scale (CSSS).
- Neurocognitive battery – consisting of the Grooved Pegboard test, the Judgment of Line Orientation, the Trailmaking Test (A&B), the Hopkins Verbal Learning Test, and the Verbal Fluency test (COWAT). And for this visit only, the Mini-Mental State Examination (MMSE), the Wechsler Abbreviated Scale of Intelligence (WASI), and the Brief Visuospatial Memory Test – Revised (BVMT-R). (20)
- Subject to be referred to his/her medical physician for a pre-operative evaluation to determine if safe to undergo surgery and anesthesia
- Global Assessment of Function (GAF, DSM-IV Axis V) of no more than 50 (to demonstrate that subject's condition is severe and disabling)
- At the conclusion of this visit, all subjects who meet all inclusion/exclusion criteria will be given an appointment card for the next study visit.

#### **4.4. Visit 2 – Baseline Visit #2**

Approximately 2 weeks after Visit #1.

At this visit, the following assessments will be performed:

- DSM-IV SCID to confirm subject has diagnosis of TS by a **different** study psychiatrist or neurologist (second evaluator), for ages 15-17 this will be the K-SADS assessment.
- Repeat TS / OCD / ADHD symptom scales: YGTSS, YBOCS, and the WHO ASRS.
- Repeat Ham-D, BAI, and YMRS for depression, anxiety, and/or mania symptoms. For ages 15-17, the Ham-D and BAI scales will be replaced with the Beck Youth Inventory.
- Urine sample for urine toxicology screen (must be negative for illicit substances for subject to continue in study)

At the conclusion of this visit, all subjects who continue to meet all inclusion/exclusion criteria will be given an appointment card for the next study visit.

#### **4.5. Visit 3 – Baseline Visit #3**

Approximately 2 weeks after Visit #2.

At this visit, the following assessments will be performed:

- Repeat TS / OCD / ADHD: YGTSS, YBOCS, and WHO ASRS.
- Repeat Ham-D, BAI, and YMRS for depression, anxiety, and /or mania symptoms. For ages 15-17, the Ham-D and BAI scales will be replaced with the Beck Youth Inventory.
- CSSS

Date: 2/24/2021

Principal Investigator: [name], PhD

Application Number: NA\_00073086

- Urine sample for urine toxicology screen (must be negative for illicit substances for subject to continue in study) and urine pregnancy test (for females).
- Schedule pre-operative diagnostic MRI and frame-based MRI (to aid with stereotactic targeting of the electrode). Head CT examinations will be used if there are contraindications to MRI.

If all 3 baseline YGTSS tic subscale scores are not at least 35 the subject will be excluded from re-evaluation for entrance into the study for 6 months. All three urine samples must be negative for illicit substances.

At the conclusion of this visit, all subjects who continue to meet all inclusion/exclusion criteria will be given an appointment card for the next study visit. **The next study visit is the neurosurgical procedure for implantation of the DBS device. The pre-operative diagnostic MRI must be performed for the subject prior to the next visit.** The neurosurgical procedure should be planned for 2 – 3 weeks after Baseline Visit #3. This pre-operative MRI may also be used for coregistration with CT imaging obtained the morning of surgery for surgical planning of the lead placement, if the patient's symptoms preclude MRI imaging with the stereotactic frame the morning of surgery.

#### 4.6. Visit 4 – Neurosurgical Procedure for Implantation of DBS System

Approximately 3 weeks after Visit #3.

At this visit, the device will be implanted by the neurosurgical study team according to standard operating procedure utilized for implantation of DBS in the subthalamic nucleus. This involves the use of a stereotactic frame, and MRI images obtained with the patient wearing the frame the morning of the surgery. If the patient's symptoms preclude MRI imaging while wearing the frame, CT imaging will be obtained instead, and these images will be coregistered with the previously acquired diagnostic MRI for target planning. The bilateral thalamic targets include the centromedian nucleus, the substantia periventricularis, and the nucleus ventro-oralis internus. The target is calculated relative to the AC-PC line using an atlas based approach. We will determine the location of the midpoint of the AC-PC and then target a point lateral by 5 mm, and posterior by 4 mm remaining in the same plane as the AC-PC line. This target was adapted from the previous study of Ackermans et al. (2). An additional aid in localization will be the use of microelectrode recordings during the case to identify thalamic bursting cells. This has been performed by our operative team in standard thalamic placement of DBS electrodes for the treatment of tremor (34).

The surgical procedure will be performed under local and IV sedation. If the patient's symptoms preclude this, the procedure will be performed under general anesthesia (this would typically be in the context of large amplitude tics making long time positioning on the operative table unsafe). For subjects undergoing general anesthesia, the FDA approved Clearpoint DBS placement system (MR Interventions) will be used in one of the iMRIS operating room suites, or the Leksell frame in the non-MRI equipped operating rooms. Fluoroscopy will be used in the operating room to check for lead placement or lead migration during the placement procedure. The fluoroscopy unit is draped into the surgical field, and arranged for lateral views of the skull.

A head CT examination immediately after the lead placement procedure will be obtained while the patient is still wearing the stereotactic frame (this is our standard procedure for other movement disorder DBS cases). This will allow us to check for hemorrhage, the amount of pneumocephalus, and lead placement. The operating room will be reserved, and the operative field kept sterile should the need arise to revise the

Date: 2/24/2021

Principal Investigator: [name], PhD

Application Number: NA\_00073086

lead positioning or evacuate a hemorrhage. The frame will be removed once the head CT examination is cleared by the operative surgeon.

A neurocritical care team will stabilize and monitor the patient in the postoperative period.

The required study documentation must be filled out by the neurosurgical team:

- Surgery Form
- Adverse events

After the subject is stable and discharged, the subject will be given an appointment card for the next study visit. **The neurostimulator will be implanted under the chest wall at the next visit.**

#### **4.7. Visit 5 – Implantation of the Neurostimulator**

Approximately 1 week after Visit #4.

Approximately one week after the subject is discharged from the hospital from the neurosurgical implantation, the subject will return for implantation of the neurostimulator under the chest wall. The intracranial electrode will be connected to the neurostimulator plus battery that powers the electrode.

The following assessments will be conducted:

- New/changed adverse events
- Record changes in concomitant medications
- TS and associated condition symptom scales (YGTSS, YBOCS, and the WHO ASRS). Repeat Ham-D, BAI, and YMRS for depression, anxiety, and /or mania symptoms. For ages 15-17, the Ham-D and BAI scales will be replaced with the Beck Youth Inventory.
- Schedule post-operative diagnostic MRI of the brain (to assess lead placement prior to implantable pulse generator programming). A head CT will be obtained if there are MRI contraindications.

At the conclusion of this visit, the subject will be given an appointment card for the next study visit.

#### **4.8. Visits 6 – 9 – Follow-up/Optimization of Programming**

These visits begin approximately 3 weeks after Visit #5.

A study neurologist (with experience in programming DBS devices who has extensive experience working with patients with movement disorders undergoing DBS) in conjunction with one of the study psychiatrists will set initial stimulation parameters. As this procedure is experimental, the stimulation parameters will be modified empirically and individualized for each subject. However, attempts will be made to use typical clinical ranges for DBS of the thalamus (electrode voltage 1 – 5.0 V, pulse width 60-210 microseconds, and stimulation frequency 130 – 185 Hz (35). These numbers indicate the ranges and maxima for the stimulation parameters to be used in this protocol. These represent conservative values with respect to the safety of the stimulation, as indicated by the limits incorporated into the Medtronic programmer. The study neurologist experienced in programming in conjunction with one of the study psychiatrists will use TS symptom scales (especially the Severity Ratings section of the YGTSS, incorporating measures of tic frequency and intensity) to optimize the DBS programming at all subsequent follow-up visits. In situations of partial response as assessed over the previous week, the stimulation voltage intensity may be increased,

Date: 2/24/2021

Principal Investigator: [name], PhD

Application Number: NA\_00073086

or the frequency and pulse width settings modified within the limits stated above to seek a more complete response. Any acute changes in OCD or ADHD symptoms, acute changes in depression or anxiety symptoms, and/or appearance of adverse events deemed likely to be related to DBS programming may prompt a reduction in stimulation voltage, change in stimulation contacts used, or alteration in frequency or pulse width.

At the time of initial programming, the subjects will receive additional literature as well as the appropriate patient controller device, which allows them to turn the stimulation on or off. The subjects will be instructed in its use and receive pocket cards and materials to carry with them.

The subject will come in for four further follow-up visits weekly after the initial programming session (Visit #6). The study neurologist experienced in programming in conjunction with one of the study psychiatrists will use TS symptom scales (especially YGTSS), acute changes in OCD or ADHD symptoms, acute changes in depression or anxiety symptoms, and/or appearance of adverse events deemed likely to be related to DBS to optimize programming at all subsequent follow-up visits.

The following assessments will be conducted:

- Programming Form
- New/changed adverse events
- Record changes in concomitant medications
- TS symptom scales ( YGTSS, YBOCS, WHO ASRS)
- Ham-D, BAI, and YMRS for depression, anxiety, and/or mania symptoms (Beck Youth Inventory for ages 15-17)
- CSSS at alternating visits.
- Global Assessment of Function Scale (GAF)
- Neurocognitive battery (as per Visit #1)

At the conclusion of this visit, the subject will be given an appointment card for the next study visit.

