#### **4.10. Visit 13 – Study Completion (or Early Termination Visit)**

This visit is approximately 4 months after Visit #12.

The purpose of this last visit is to monitor for symptom changes, report any complications and to optimize programming if necessary. Subjects will come in at 4 months after the last visit (12 months after implantation of the neurostimulator). The study neurologist experienced in programming in conjunction with one of the study psychiatrists will use TS symptom scales (YGTSS, YBOCS, and the WHO Adult ADHD Self-Report Scale), acute changes in depression or anxiety symptoms, and appearance of adverse events deemed likely to be related to DBS to optimize programming at all subsequent follow-up visits.

The following assessments will be conducted at study completion (or if the subject is early terminated from the study for any reason):

- Programming Form
- New/changed adverse events
- Record changes in concomitant medications
- TS symptom scales (YGTSS, YBOCS, and the WHO ASRS)
- Ham-D, BAI, YMRS (Beck Youth Inventory for ages 15-17)
- GAF
- Neurocognitive battery (as per Visit #1)

At the conclusion of this visit, the subject will be discharged from the study and will continue standard clinical care for patients who undergo DBS procedures. The patient will continue to meet with the study physicians. If symptom improvement has been observed with DBS, the patient will continue standard of care for DBS. If symptom improvement has not been observed, the subject can opt to have the stimulation device turned off.

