#### **4.14 Long-Term Follow-Up Visits**

The purpose of the long-term follow-up visits is to monitor for additional symptom changes, report any complications and to optimize programming if necessary over the lifetime of the implanted system. Subjects will come in at roughly 6 month intervals for two years after Visit #13, and then annually after that. The study neurologist experienced in programming in conjunction with one of the study psychiatrists will use TS symptom scales (especially the YGTSS), acute changes in other comorbid conditions (OCD/ADHD), acute changes in depression or anxiety symptoms, and/or appearance of adverse events deemed likely to be related to DBS to optimize programming at all subsequent follow-up visits. These assessments will occur until the subject no longer wants to participate, or until the device is removed due to a complication or wish of the subject, or until the device generator depletes and the subject no longer wishes to have it replaced.

Replacements for the IPG will be performed when the cell is depleted as assessed during follow-up visits or for changes in symptoms. The first cell implanted at Visit #5 will be the Activa PC (standard cell). Either the Activa PC (standard cell) or the Activa RC (rechargeable system) will be offered at the times of IPG replacement subsequent to this, pending the subject's preference and willingness to participate in the recharging process. The RC system will be discussed with the subject particularly in cases where the lifetime of the prior IPG was less than 2 years.

The following assessments will be conducted:

- Programming Form
- New/changed adverse events
- Record changes in concomitant medications
- TS symptom scales (YGTSS, YBOCS, WHO ASRS)
- Ham-D, BAI, YMRS (Beck Youth Inventory for ages 15-17)
- GAF
- CSSS at alternating visits.
- Neurocognitive battery if suggested for any reason by one of the study neurologists or psychiatrists

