### **7.5. Early Stopping Rules**

Date: 2/24/2021

Principal Investigator: [name], PhD

Application Number: NA\_00073086

DBS will be discontinued if the subject experiences a worsening of his tic or other Tourette symptoms (or OCD, ADHD, depression, or anxiety symptoms) without returning to baseline (prior to DBS implantation) within 4 weeks from the worsening of the symptoms. DBS will be discontinued if subjects experience suicidal ideation or mania that does not improve with turning off the stimulator. DBS will also be discontinued if neurologic symptoms including muscle contractions, flashing lights, electric jolting sensations, increase in dyskinesias will not improve with stimulator setting change and they are severe enough to interfere with patient daily functioning. Finally DBS will be discontinued if subjects are unable to tolerate the stimulator for any reason not foreseen by the investigator and that clearly interferes with subject's functioning.

Subjects will also be removed from the study for any significant adverse events that jeopardize patient safety. This includes any events related to the surgical procedure or subsequent DBS stimulation therapy. The entire study of 10 subjects will be stopped should the number of subjects meeting the above **Early Stopping Rules** reaches 3 at any point in the study. If this occurs before the full subject recruitment goal has been met, no further subjects will be recruited.

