#### **8.4. Disclosing reportable findings and parental notification**

The following set of ground rules to use in terms of informing parents of the 15-17 year age range study subjects about concerning results from the psychiatric assessments, or revelations of high risk behaviors will be implemented in this study:

We assess for suicidal thoughts at multiple visits in the protocol (using the CSSS), if we are concerned about the child based on the answers to this assessment, the parents will be informed and a discussion will be had with the parents and the child to gain more information. Additional treatment providers will be contacted (child psychiatry) if the child does appear to be at risk of hurting himself/herself.

Assessments during the study visits also include questions concerning drug and alcohol use. This information will be kept private and not disclosed to the parent or authorities unless there are serious concerns about the child's safety or the safety of others. If the child provides study staff with information indicating that imminent harm to self and/or others is possible as a result of drug and alcohol use (for example, substance use while driving, binge behaviors, risky and unprotected sexual contact under the influence, etc.), then the parents will be informed.

Any information regarding child abuse, reportable communicable diseases, and any possible threats of harm to the subject or others (for example suicide and homicide) will be disclosed to the parent(s) or the appropriate authorities depending on the circumstance.

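### The suicidality scale is scheduled at only four of nine visits from Visit 5 to Visit 13 and not at early termination, although suicidal ideation is a discontinuation ground and the mania scale is listed at all nine

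*Combined protocol and SAP*

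**What the plan says.** **Rule.** Section 7.5 states: "DBS will be discontinued if subjects experience suicidal ideation or mania that does not improve with turning off the stimulator". It then adds a study-level consequence: "The entire study of 10 subjects will be stopped should the number of subjects meeting the above" stopping rules reaches 3. Safety is one of the two primary objectives (section 2.1).

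**Instrument.** Section 8.4, on subjects aged 15 to 17, says: "We assess for suicidal thoughts at multiple visits in the protocol (using the CSSS"). Whether parents are informed depends on the answers to that scale.

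**Schedule.** Sections 4.8 (Visits 6 to 9), 4.9 (Visits 10 to 12) and 4.14 (long-term follow-up) each list "CSSS at alternating visits". Table 4.12 places the scale at Visits 1, 3, 6, 8, 10 and 12. Section 4.7 (Visit 5) does not list it. Section 4.10 (Visit 13, also used for early termination) does not list it either, but has "Ham-D, BAI, YMRS (Beck Youth Inventory for ages 15-17"). The YMRS appears at every visit with rating scales, with no alternation.

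**Long-term spacing.** Section 4.14: "Subjects will come in at roughly 6 month intervals for two years after Visit #13, and then annually after that". It does not say at which long-term visit the alternation starts.

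**The concern.** Suicidal ideation and mania stand in one sentence of section 7.5 with the same consequence. One has a rating scale at every visit with scales. The other has its named scale at fewer than half of the visits from Visit 5 to Visit 13, and the protocol gives no reason for the difference. Subjects attend the skipped visits anyway and complete a long battery there.

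Two consequences follow.

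- A stimulation change made at a visit where the CSSS is given (6, 8, 10 or 12) is not followed by a CSSS at the next scheduled visit.
- A subject who leaves early, possibly because of suicidal ideation, completes the section 4.10 assessments, and these contain no CSSS.

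What is at stake is the completeness of structured suicidality data under a primary safety objective, in a study of 10 subjects where each case counts.

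**Working it through.** The protocol states no CSSS interval, so there is no figure of its own to reproduce. The inputs are the study weeks in table 4.12 and the spacing in section 4.14.

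| Visit | Week | CSSS | YMRS |
|---|---|---|---|
| 3 | 4 | yes | yes |
| 5 | 8 | no | yes |
| 6 | 11 | yes | yes |
| 7 | 12 | no | yes |
| 8 | 13 | yes | yes |
| 9 | 14 | no | yes |
| 10 | 23 | yes | yes |
| 11 | 35 | no | yes |
| 12 | 47 | yes | yes |
| 13 | 62 | no | yes |

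(Visit 4 is lead surgery, with no scales.)

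**Coverage, Visits 5 to 13.** CSSS at 4 of 9 visits; YMRS at 9 of 9.

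**CSSS gaps.** 11 − 4 = 7 weeks (spanning both operations), 13 − 11 = 2, 23 − 13 = 10, 47 − 23 = 24. The text timing agrees: months 3 and 9 after implantation are 6 months apart, about 26 weeks.

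**YMRS gaps from Visit 5.** 3, 1, 1, 1, 9, 12, 12 and 15 weeks. The longest is 62 − 47 = 15.

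**Which stimulation changes wait.** After Visits 7, 9 and 11 the next visit (8, 10, 12) has a CSSS. After Visits 6, 8 and 10 the next visit (7, 9, 11) has none, and the score comes two visits later, at weeks 13, 23 and 47. After Visit 12 the next visit, 13, also has none.

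**Long-term.** Take 6 months as 26 weeks and 1 year as 52. Visits then fall at weeks 88, 114, 140 and 166, and at 218, 270, 322 and so on.

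- Alternation starting at the first long-term visit: CSSS at 88, 140, 218, 322. Gaps from week 47: 41, 52, 78, 104.
- Starting at the second: CSSS at 114, 166, 270. Gaps from week 47: 67, 52, 104.

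**Average wait, as an illustration.** Assume onset uniform over weeks 11 to 47 (36 weeks). Mean wait to the next scheduled CSSS = Σ(gap²) / (2 × 36).

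- As planned: (2² + 10² + 24²)/72 = 680/72 = 9.4 weeks.
- At every visit: (1 + 1 + 1 + 81 + 144 + 144)/72 = 372/72 = 5.2 weeks.
- Adding Visit 11 only: (4 + 100 + 144 + 144)/72 = 392/72 = 5.4 weeks. This is (680 − 392)/(680 − 372) = 288/308 = 94% of the saving.

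For onset uniform over weeks 47 to 62 (midpoint 54.5), the mean wait is 88 − 54.5 = 33.5 or 114 − 54.5 = 59.5 weeks as planned. With a CSSS at Visit 13 it is 62 − 54.5 = 7.5 weeks. Visits 11 and 13 therefore carry most of the gain in the main study period.

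**The case against.** The best reply is that time to the next CSSS is not time to detection.

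- New or changed adverse events are recorded at every follow-up visit, and section 8.3 names suicidal ideation as an example.
- A study psychiatrist takes part in programming throughout, looking at acute changes in depression and at adverse events.
- Unscheduled visits under section 4.13 include the CSSS.
- Section 5.3 excludes subjects with a current or past suicidal plan or intent.
- Text and table agree on Visits 6, 8, 10 and 12, so this is a choice and not a contradiction.

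Most of this stands, and it limits the point. It does not close the gaps. Unscheduled visits depend on the subject calling. Adverse-event recording is not the structured instrument that section 8.4 names. The exclusion concerns history at entry, while section 7.5 concerns ideation arising under stimulation. Mania can also be reported as an adverse event, yet it is still scored each time. The Ham-D or the Beck Youth Inventory is given at each visit with scales, but the protocol does not assign either to suicidality, and I have not relied on their content.

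A reader might infer three stronger things that the documents do not support.

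- *That changes at Visits 7, 9 or 11 wait longest for a score.* Each of these is followed by a CSSS at the very next visit.
- *That the study-stop count captures suicidality half as often as its other grounds.* Section 7.5 sets no CSSS threshold, so ideation reported as an adverse event can meet the rule.
- *That the two-year gap applies to all long-term follow-up.* It applies only once visits are annual.

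**Conclusion.** The point holds as a gap in scheduled, structured measurement that is cheap to close. From Visit 5 to Visit 13 the CSSS is given at 4 of 9 visits where the YMRS is given at all 9. The longest gap between scheduled scores is 24 weeks (weeks 23 to 47). There is none at week 62 or at early termination. The next score after week 47 is about 41 to 67 weeks away, depending on where the alternation starts. Gaps are then about one year in the 6-monthly phase and two years in the annual phase, with one 78-week transition if the alternation starts at the first long-term visit.

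The gap figures rest on the nominal weeks in table 4.12 and on 26-week half-years. The mean waits also assume uniform onset, which nothing in the protocol supports, and they do not estimate delay to clinical recognition. The documents do not show that suicidal ideation would go unnoticed or that the stopping rule would fail.

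**What to change.** List the CSSS at every post-implantation visit where the YMRS is already listed: Visits 5 to 13, including early termination, and every long-term visit.

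- Sections 4.8, 4.9 and 4.14: replace the alternating-visit entry with the CSSS at each visit.
- Sections 4.7 and 4.10: add the CSSS. Section 4.11 refers to the 4.10 list, so early termination is then covered.
- Table 4.12: add the CSSS to the rows for Visits 5, 7, 9, 11 and 13.

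Stopping at Visit 12 would not be enough. It would leave about 41 weeks (week 47 to 88) without a scheduled score, longer than the present 24-week gap.

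With the full change, the longest scheduled gap through week 62 is 15 weeks (Visit 12 to 13). Long-term gaps become about 26 weeks for two years and 52 weeks after that. If burden is a concern, Visits 11 and 13 matter most before long-term follow-up.

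The cost is a few more minutes at visits already planned, with an instrument already in use. This changes measurement only; the discontinuation and study-stop rules stay as written.
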